Table 6-2.	Schedule of Assessments for Cohort 3	43

PROTOCOL SYNOPSIS

Gilead Sciences, Inc.
[name]
[name]

Study Title: A Phase 2b, Open-Label Study of 200 mg or 400 mg Sofosbuvir+RBV for 24 Weeks in Genotype 1 or 3 and Ledipasvir/Sofosbuvir (LDV/SOF) Fixed-Dose Combination (FDC) Tablet for 12 weeks in Genotype 1 or 4 HCV-Infected Subjects with Renal Insufficiency

IND Number: 106739

Eudra CT Number: 2013-002897-30

Study Centers Planned: Multiple sites in New Zealand, Europe, North America and South America

Number of Subjects Planned: Approximately 35 subjects

Target Population: Adults with chronic renal insufficiency and HCV infection

Treatment Duration: 12 weeks or 24 weeks

Objectives: The primary objectives of this study are:

- To evaluate the safety of sofosbuvir (SOF) 200 mg or 400 mg + ribavirin (RBV) for 24 weeks and LDV/SOF for 12 weeks as assessed by review of the accumulated safety data in each treatment arm
- To evaluate the efficacy of sofosbuvir (SOF) 200 mg or 400 mg + ribavirin (RBV) for 24 weeks and LDV/SOF for 12 weeks measured by the proportion of subjects with renal insufficiency who have achieved a sustained viral response 12 weeks after treatment discontinuation (SVR12) in each treatment arm
- To evaluate the steady state pharmacokinetics of SOF and its metabolites and LDV upon dosing SOF 200 mg or 400 mg or LDV/SOF in subjects with renal insufficiency

The secondary objectives of this study are:

- To evaluate the proportion of subjects with renal insufficiency who attain SVR at 4 and 24 weeks after discontinuation of treatment (SVR4 and SVR24)
- To evaluate the kinetics of plasma HCV RNA during and after treatment discontinuation
- To evaluate the emergence of viral resistance to SOF and LDV during and after treatment discontinuation

The exploratory objective of this study is:

PPD [REDACTED]

Study Design:

This study will enroll approximately 35 subjects with severe renal insufficiency.

- Cohort 1: 10 subjects will receive SOF 200 mg QD + RBV 200 mg QD for 24 weeks.
- Cohort 2: Following review of safety, efficacy and PK data through post-treatment Week 4 of Cohort 1, 10 additional subjects will receive SOF 400 mg QD + RBV 200 mg QD for 24 weeks.
- Cohort 3: Following review of safety and available PK data through Week 12 of Cohort 2, 15 additional subjects will receive LDV/SOF QD for 12 weeks.

Diagnosis and Main Eligibility Criteria:

Adults (≥ 18 years) with chronic genotype 1 or genotype 3 (for Cohorts 1 and 2) or genotype 1 or 4 (for Cohort 3) HCV infection. Reference Sections 4.2 and 4.3 for detailed Inclusion and Exclusion criteria.

**Study Procedures/
Frequency:**

Screening assessments will be completed within 42 days of the Day 1 visit.

Study visits will occur at Screening, Day 1, and at the end of Weeks 1, 2, 4, 6, 8, 10, 12 (all cohorts), and Weeks 16, 20 and 24 (Cohorts 1 and 2 only) and at Post-Treatment Weeks 4, 12, and 24 (all cohorts). Screening assessments will include physical examination, height, weight, vital signs, 12-lead ECG, echocardiogram, concomitant medications, safety laboratory tests,

HCV RNA, serology (HIV, HCV, HBV), hemoglobin A1c (HbA1c), serum β -hCG (females of child bearing potential only), IL28B genotyping.

On-treatment assessments will include adverse events (AEs), concomitant medications, study medication pill count, physical examination, vital signs, 12-lead ECGs, echocardiogram, safety laboratory tests, HCV RNA, pharmacokinetic samples, and serum pregnancy tests (females of child bearing potential only).

Post-treatment assessments will include AEs, concomitant medications, vital signs, safety laboratory tests, HCV RNA, and serum pregnancy tests (females of child bearing potential only).

Samples for viral RNA sequencing will be collected at Day 1 and every visit thereafter. Samples will be collected during treatment visits for PK analysis of study drug(s).

PK assessments

Intensive PK Assessments

Cohorts 1 and 2:

Serial blood samples will be collected on week 2 and 12 at the following timepoints:

- 0 (pre-dose -5 minutes), 0.25, 0.5, 1, 2, 4, 6, 8, 10, and 12 hours post-dose.

Cohort 3:

Serial blood samples will be collected once either on week 2 or 4 (per investigator discretion) at the following timepoints:

- 0 (pre-dose -5 minutes), 0.25, 0.5, 1, 2, 4, 6, 8, 10, and 12 hours post-dose.

Plasma concentrations of SOF and its metabolites and LDV will be determined and PK parameters will be estimated as appropriate. Plasma concentrations of RBV may be determined, if necessary.

Trough PK Assessments:

Trough PK plasma samples for analyses of SOF, its metabolites, RBV (as applicable) and LDV concentrations will be collected at all other on treatment visits beginning at the Week 1 visit.

PK Parameters for SOF, its metabolites, LDV and RBV will be estimated as appropriate.

Optional Genetic Sample Collection

PPD

Archived Plasma Sample

Archive plasma samples are being collected for possible additional analyses, including but not limited to, study drug or metabolite measurements, viral load, safety/efficacy assessments, HCV gene sequencing, HCV resistance testing and other possible predictors of response as determined by Gilead.

Test Product, Dose, and Mode of Administration:

Sofosbuvir is manufactured as 100 mg and 400 mg tablets for oral administration. Subjects enrolled to take the 200 mg dose will take 2 × 100 mg tablets for a total dose of 200 mg orally QD in the morning with RBV and with food. Subjects enrolled to take the 400 mg dose will take 1 × 400 mg tablet for a total dose of 400 mg orally QD in the morning with RBV and with food.

RBV will be supplied as a 200 mg tablet for oral administration by Gilead Sciences. Subjects will take 1 × 200 mg tablet in the morning with SOF and with food.

LDV/SOF is manufactured as a fixed-dose combination tablet, consisting of 90 mg LDV and 400 mg SOF, for oral administration. All subjects will take 1 tablet daily with or without food.

Reference Therapy:

None

Criteria for Evaluation:

Safety: AEs, SAEs, and safety labs will be collected throughout the study. Safety will be evaluated by assessment of clinical laboratory tests, ECG, echocardiogram, periodic physical examinations including vital signs at various time points during the study, and by the documentation of adverse events.

Efficacy: Efficacy will be evaluated using scheduled assessments of HCV RNA performed using COBAS® AmpliPrep/COBAS® TaqMan® HCV Test.

PK: Plasma PK parameters will be calculated for sofosbuvir and its metabolites GS-566500 and GS-331007, LDV and RBV, as applicable. Examples are AUC_{last} , AUC_{tau} , C_{max} , C_{last} , C_{tau} , and $t_{1/2}$.

Statistical Methods:

Safety data will be listed by subject and summarized by treatment cohort using frequency of event/abnormality or descriptive statistics (e.g., sample size, arithmetic mean, geometric mean, % coefficient of variation [CV], standard deviation [SD], minimum, Q1, median, Q3, and maximum).

The steady state PK plasma concentrations and parameters will be listed by subject and summarized by treatment cohort using descriptive statistics for each analyte (SOF, GS-566500, GS-331007, RBV and LDV, as appropriate).

In the efficacy analysis, no statistical hypothesis testing will be performed and no formal inferences will be made on the primary efficacy endpoint SVR12. A point-estimate with two-sided 95% exact confidence interval (CI) using the binomial distribution (Clopper-Pearson method) will be constructed for the SVR12 rate by treatment cohort. Similar analysis will be also performed for secondary endpoints SVR4 and SVR24.

To evaluate the kinetics of circulating HCV RNA during and after treatment discontinuation, viral load data will be listed by subject and summarized by treatment cohort and visit using descriptive statistics.

Due to the exploratory nature of this study, no formal power or sample size calculations were performed to determine treatment group size. The total sample size of 35 is largely based on feasibility.

This study will be conducted in accordance with the guidelines of Good Clinical Practices (GCPs) including archiving of essential documents.

GLOSSARY OF ABBREVIATIONS AND DEFINITION OF TERMS

°C	degrees Celsius
°F	degrees Fahrenheit
β-hCG	β-human chorionic gonadotropin
AE	adverse event
ALT	alanine aminotransferase (also SGPT)
ANC	absolute neutrophil count
APTT	activated partial thromboplastin time
AST	aspartate aminotransferase (also SGOT)
AUC	area under the curve
AUC _{tau}	area under the plasma concentration versus time curve over the dosing interval (tau)
BID	twice a day
BLQ	below the lower limit of quantification
BMI	body mass index
BW	body weight
CL _{cr}	Creatinine clearance
C _{max}	the maximum observed serum/plasma/peripheral blood mononuclear (PBMC) concentration of drug
C _{tau}	observed drug concentration at the end of the dosing interval (tau)
CRF	case report form(s)
CRO	Contract (or clinical) research organization
DAA	direct-acting antiviral
dL	Deciliter
DNA	deoxyribonucleic acid
DSPH	Drug Safety and Public Health
ECG	Electrocardiogram
eCRF	Electronic case report form(s)
ESAs	Erythropoiesis stimulating agents
ESRD	End Stage Renal Disease
EU	European Union
FAS	full analysis set
FDA	(United States) Food and Drug Administration
FEV ₁	forced expiratory volume in one second
GCP	Good Clinical Practice (Guidelines)
GGT	gamma glutamyl transferase
GSI	Gilead Sciences, Inc.
GT	Genotype (viral)
Hb	Hemoglobin
HbA _{1c}	Hemoglobin A _{1c}

GLOSSARY OF ABBREVIATIONS AND DEFINITION OF TERMS (CONTINUED)

HBV	Hepatitis B virus
HCV	Hepatitis C virus
HDPE	high-density polyethylene
HIV	Human Immunodeficiency Virus
HLGT	High-Level Group Term
HLT	High-Level Term
IBW	Ideal Body Weight
ICH	International Conference on Harmonisation
IEC	independent ethics committee
IL28B	IL28B gene
IND	Investigational New Drug (Application)
IRB	institutional review board
IUD	intrauterine device
IV	Intravenous
kg	Kilogram
L	Liter
LDH	Lactase dehydrogenase
LDV	Ledipasvir
LLN	lower limit of the normal range
LLOD	Lower limit of detection
LLOQ	Lower limit of quantification
LLT	Lower-Level Term
MedDRA	Medical Dictionary for Regulatory Activities
Mg	Milligram
MH	Mantel-Haenszel
mL	Milliliter
Min	Minute
mmHg	millimeters mercury
NS (3/4A/5A/5B)	Non-structural Protein
PBMC	peripheral blood mononuclear cell(s)
PEG	Pegylated interferon
P-gp	P-glycoprotein
PI	Protease inhibitor
PK	Pharmacokinetic
po	Per os (by mouth)
QD	once daily (use only in tables)
QTcF	QT interval corrected using Fridericia's formula
RBC	Red blood cell count

GLOSSARY OF ABBREVIATIONS AND DEFINITION OF TERMS (CONTINUED)

RBV	Ribavirin
RNA	ribonucleic acid
RVR	rapid virologic response
SADR	Serious adverse drug reaction
SAE	serious adverse event
SD	Standard deviation
SOC	Standard of Care
SOF	Sofosbuvir
SOP	Standard operating procedure
SUSAR	Suspected Unexpected Serious Adverse Reaction
SVR	Sustained Virologic Response
t_{\max}	The time (observed time point) of C_{\max}
TND	Target not detected
TSH	Thyroid stimulating hormone
$t_{1/2}$	An estimate of the terminal elimination half-life of the drug in serum/plasma/PBMC, calculated by dividing the natural log of 2 by the terminal elimination rate constant (λ_z)
ULN	upper limit of the normal range
US	United States
WBC	white blood cell count

1. INTRODUCTION

1.1. Background

Hepatitis C virus (HCV) is responsible for a large proportion of chronic liver disease worldwide and accounts for 70% of cases of chronic hepatitis in industrialized countries. The global prevalence of chronic hepatitis C is estimated to average 3% {23338}. The most common genotype worldwide is genotype 1 followed by genotypes 2 and 3 {23338}. Although there is evidence that the incidence of viral infection may be decreasing, the prevalence of liver disease caused by HCV is on the rise, primarily due to the lag between the onset of infection and the clinical manifestation of liver disease {23338}. The prevalence of chronic HCV is significantly higher among patients with chronic renal failure, and HCV itself is associated with impaired renal function. Treatment of these individuals is therefore recommended but is often complicated by the substantial increase in hematologic toxicities associated with the use of ribavirin in the setting of low creatinine clearance {23275}.

1.2. Sofosbuvir (formerly GS-7977)

Sovaldi® (sofosbuvir) is a potent nucleotide analogue that inhibits HCV RNA replication in vitro and has demonstrated high rates of sustained viral response (SVR) when administered with RBV, with or without pegylated interferon, to subjects with chronic genotype 1-6 HCV infection {34475}, {23275}, {24713}, {24715}, {27832}. Sovaldi® has been approved in the United States (GT1-4) and in the European Union (GT1-6) for the treatment of chronic HCV infection including treatment naïve and experienced patients and HIV/HCV co-infected patients.

For further information on the clinical pharmacology, virology, safety and efficacy of sofosbuvir (SOF), please refer to the current version of the Investigator's Brochure and US and EU prescribing information.

1.3. Ribavirin (RBV)

Ribavirin is a guanosine analogue that inhibits the in vitro replication of a wide range of RNA and DNA viruses {15572}, {15668}. Ribavirin monotherapy has little or no effect on the replication of HCV but can result in short term normalization of serum ALT activity. When combined with interferon or PEG therapy, RBV decreases substantially the relapse rate seen after cessation of interferon therapy {12557}, {12558}.

Ribavirin is a known teratogen (FDA category X). Furthermore, RBV is known to accumulate intracellularly where it is cleared slowly, and is also excreted in semen. Therefore, extreme care must be taken to avoid pregnancy during RBV therapy and for up to 6 months following completion of treatment. A comprehensive review of RBV is contained in the package insert/SmPC.

1.4. Ledipasvir/Sofosbuvir Fixed-Dose Combination

Harvoni® (ledipasvir/sofosbuvir fixed-dose combination (LDV/SOF) combines two HCV specific-direct acting antiviral (DAA) agents into a single tablet for the treatment of chronic HCV infection. Sofosbuvir is a nucleotide analog that is a potent and selective inhibitor of NS5B-directed HCV replication, irrespective of HCV genotype. Ledipasvir is a novel HCV NS5A inhibitor that has demonstrated potent anti-HCV activity against genotypes 1 and 4 HCV infection. Harvoni® has been approved in the United States and Europe for the treatment of chronic HCV infection including treatment naïve and experienced patients with genotype 1.

For further information on the clinical pharmacology, virology, safety and efficacy of LDV/SOF, please refer to the current version of the Investigator's Brochure and US prescribing information.

1.5. Preliminary Results of Study GS-US-334-0154, Cohort 1

Preliminary results are available and presented below for Cohort 1: 10 subjects with estimated glomerular filtration rate (eGFR by Cockcroft-Gault) less than 30 mL/min within six months of screening, not on dialysis, treated with SOF 200 mg + RBV 200 mg daily for 24 Weeks. A review of the integrated safety, PK and efficacy from this first cohort demonstrate that SOF 200 mg + RBV 200 mg daily for 24 weeks is safe and relatively well tolerated.

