1.6. Rationale for the Current Study

This study will evaluate the safety, efficacy and pharmacokinetics of treatment with SOF+RBV for 24 weeks (for genotype 1 or 3) and of treatment with LDV/SOF for 12 weeks (for genotype 1 or 4) in subjects with chronic HCV infection and severe renal impairment.

Interferon monotherapy, however, is associated with poor tolerability, a 48 week treatment duration, and efficacy of approximately 40%. Furthermore, once patients have failed this course of treatment, they have no further treatment options and are at risk for progression of liver disease, cirrhosis, and hepatocellular carcinoma.

1.6.1. Cohorts 1 and 2

To date, SOF+RBV has demonstrated safety and efficacy in a broad range of subjects with chronic HCV infection in Phase 2 and Phase 3 clinical trials. However, subjects with Cr clearance <60 mL/min have been excluded from these studies due to the recommendation that RBV not be administered to patients with Cr clearance <50 mL/min. In addition, study P7977-0915 has shown the major circulating metabolite of SOF, GS-331007, is renally cleared and a single dose study conducted in subjects with severe renal impairment or end-stage renal disease on hemodialysis demonstrated exposures approximately 1.6-fold and 14 to 22-fold higher, respectively, than those observed in matched controls with normal renal function. Whilst dose reduction of SOF would reduce these exposures, viral efficacy is dependent on SOF exposures such that lower SOF doses or intermittent administration could be associated with reduced efficacy. Thus, this exploratory study of safety and efficacy of standard (400 mg) and reduced (200 mg) doses of SOF in combination with low-dose RBV in a small number of subjects will provide important data regarding dosing recommendations for use of SOF in this patient population with a high unmet medical need.

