1.7. Rationale for SOF Dose Selection

Sofosbuvir 400 mg, once daily, when dosed in combination with RBV with or without PEG has demonstrated broad genotypic efficacy and a favorable safety profile in over 3300 HCV-infected subjects across multiple patient populations in Phase 2 and 3 trials. This dose (400 mg) is the proposed to be marketed dose of sofosbuvir for the treatment of HCV-infection.

In study P7977-0915, a single dose PK study in subjects with varying degrees of renal impairment, exposure (AUC_{inf}) of sofosbuvir and the renally eliminated metabolite, GS-331007, were 2.7- and 5.5-fold higher respectively in subjects with severe renal impairment compared to matched controls with normal renal function. A significant dose reduction (eg, 2- to 4-fold) of sofosbuvir would be necessary to provide comparable GS-331007 exposures in subjects with severe renal impairment and those with normal renal function. Data from dose-finding and Phase 2 studies demonstrated that sofosbuvir, dosed once daily, was necessary to provide the active anabolite at the site of action (circulating GS-331007 cannot be phosphorylated to the active anabolite); therefore, dose interval modifications may not be appropriate. The efficacy of a substantially reduced dose of sofosbuvir in subjects with severe renal impairment has not been established.

Cohorts 1 and 2 of this study will evaluate the safety, efficacy and pharmacokinetics of 2 doses of sofosbuvir (200 and 400 mg) in subjects with severe renal impairment. The reduced dose of 200 mg sofosbuvir provided comparable systemic exposures of sofosbuvir, and approximately 4-fold higher GS-331007 exposure compared to HCV-infected in subjects with normal renal function at the 400 mg dose. As such, GS-331007 and SOF exposures in Cohort 2 (400 mg SOF) are expected to increase 2-fold over that observed in Cohort 1. Review of safety, efficacy and pharmacokinetic data from Cohort 2 through 12 weeks of treatment will inform the initiation of Cohort 3 (90/400 mg LDV/SOF in subjects with severe renal impairment).

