1.8. Rationale for RBV Dose Selection

Ribavirin increases treatment response rates when administered with interferon or PEG. In addition, reducing the RBV dose from 1000-1200 mg/day to 600 or 800 mg/day when given in combination with SOF reduced SVR rates, as did SOF monotherapy. It is therefore desirable to keep RBV as part of the SOF treatment regimen. Since RBV is cleared renally and its main toxicity is hemolytic anemia which is poorly tolerated in patients with advanced renal insufficiency who are usually anemic at baseline and have little bone marrow reserve, the

starting dose of RBV must be substantially lower than 1000-1200 mg/day. For this study, a dose of 200 mg/day has been selected based on investigator input in light of the high frequency of hemotoxicity of RBV and the general desire to optimize the efficacy of the treatment regimen {24149}.

To date there has been no safety signal identified that is attributable to SOF when administered as part of a combination regimen. Furthermore, SOF does not exacerbate the toxicities associated with RBV, most notably hemolytic anemia. Clinical data with SOF in severe renal insufficiency and in subjects requiring hemodialysis is limited to a single dose study in non-HCV infected subjects. No specific safety signals were identified. The current study is designed to assess the safety and efficacy of therapeutic treatment with SOF+RBV in a small number of subjects with severe renal insufficiency.

The potential benefit of successful treatment of HCV in these subjects is substantial. Few patients with severe renal insufficiency can tolerate combination therapy with PEG+RBV due to profound anemia. SVR rates to interferon monotherapy administered for 48 weeks are less than 50%. Interferon-free treatment for 24 weeks could provide substantial improvements in safety, tolerability and efficacy for individuals with chronic HCV infection.

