1.9. Rationale for Ledipasvir/Sofosbuvir Fixed Dose Combination (FDC) Dose Selection

A fixed-dose combination tablet (FDC) of ledipasvir/sofosbuvir 90/400 mg with or without RBV has demonstrated favorable safety and efficacy profiles in over 3000 HCV-infected subjects across different patient populations in Phase 2 and 3 trials. This FDC represent the marketed doses of ledipasvir and sofosbuvir (Harvoni®, LDV/SOF) approved in the US and Europe for the treatment of chronic HCV infection including treatment naïve and experienced patients with GT1.

In support of dosing LDV/SOF to HCV-infected subjects with severe renal impairment, available pharmacokinetic data has been evaluated to project mean exposures of GS-331007 and SOF that may be achieved in these subjects (Table 1-3). Overall, increased GS-331007 exposures are expected in the context of LDV/SOF as compared to SOF administered as single agent (SOF USPI and LDV/SOF NDA, Module 2.7.2). Minimal safety data is available at these high exposures, irrespective of SOF being administered with LDV or as a single agent. The study design allows for consistent progression (~2-3 fold increase) of GS-331007 exposure across cohorts enabling assessment of exposure vs. safety relationships while potentially providing greater efficacy with the two-drug combination.

Table 1-3. Observed and Predicted GS-331007 and SOF Exposure in Subjects with Renal Impairment

Mean (%CV, if applicable) PK Parameter		GS-331007		SOF	
		AUC _{tau} (ng•hr/ml)	C _{max} (ng/ml)	AUC _{tau} (ng•hr/ml)	C _{max} (ng/ml)
Observed Data	GS-US-334-0154 Cohort 1 SOF 200 mg Week 12 (n = 10)	31,100 (53.9)	1730 (44.9)	1280 (50.3)	904 (66.2)
Predicted Data	Cohort 3: LDV/SOF 90/400 mg in Severe RI ^a	111,000	4400	3430	2330

Pharmacokinetic parameters are shown to 3 significant digits

a Predicted as the LDV/SOF Phase 2/3 population multiplied times the ratio of predicted SOF 400 mg in severe RI to SOF Phase 2/3 population.

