3. STUDY DESIGN

This is a multicenter, open label study that will evaluate the safety, tolerability and antiviral efficacy of SOF with RBV or LDV/ SOF in chronic renal insufficiency and HCV infection subjects with genotype 1, 3 or genotype 4 HCV infection, including those with compensated cirrhosis.

This study will have 3 cohorts.

Approximately 35 subjects with severe renal insufficiency will be enrolled.

- Cohort 1: 10 subjects will receive SOF 200 mg QD + RBV 200 mg QD for 24 weeks.
- Cohort 2: Following review of safety, efficacy and PK data through post-treatment Week 4 of Cohort 1, 10 additional subjects will receive SOF 400 mg QD + RBV 200 mg QD for 24 weeks.
- Cohort 3: Following review of safety and available PK data through Week 12 of Cohort 2, 15 additional subjects will receive LDV/SOF QD for 12 weeks.

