3.4. Treatment Discontinuation Criteria

The Medical Monitor should be consulted prior to subject discontinuation when medically feasible. Study medication must be discontinued in the following instances:

- Unacceptable toxicity or toxicity that, in the judgment of the investigator, compromises the ability to continue study-specific procedures or is considered to not be in the subject's best interest.
- Pregnancy of female subject, or female partner of male subject.
- Efficacy failure as defined in Section 3.3.
- Declining cardiac function, defined as left ventricular ejection fraction $\leq 40\%$.
- Significant protocol violation including non-compliance with study assessments.
- Subject request to discontinue for any reason; it is important to determine whether the withdrawal of consent is primarily due to an AE, lack of efficacy or other reason.
- Discontinuation of the study at the request of Gilead, regulatory agency or an Institutional Review Board (IRB)/Independent Ethics Committee (IEC).

Subjects who discontinue treatment earlier than the assigned 12 or 24-week treatment duration will complete an Early Termination Visit (Section 6.7).

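### Eligibility would admit a subject already on dialysis, at roughly 2.5-4 times the GS-331007 exposure of severe impairment, without repeat-dose data: add an exclusion (and show dialysis in the creatinine and eGFR tables)

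*Protocol*

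**What the plan says.** **Who may enter and continue.** Protocol 4.2 item 5h requires a Cockcroft-Gault clearance of 30 mL/min or below (30-40 is allowed with a qualifying value in the previous six months). There is no lower limit. Section 4.3 lists 24 exclusions, and neither dialysis nor end-stage renal disease is among them. Section 3 describes the population in words: "Approximately 35 subjects with severe renal insufficiency will be enrolled". Section 3.4, which opens "Study medication must be discontinued in the following instances", does not list starting dialysis, and neither do the toxicity stopping rules in 7.5.1.

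**What exposure data exist.**
- Section 1.5: the ten Cohort 1 subjects had an eGFR "less than 30 mL/min within six months of screening, not on dialysis, treated with SOF 200 mg" plus ribavirin.
- Section 1.6.1: the single-dose study in severe impairment or "end-stage renal disease on hemodialysis demonstrated exposures approximately 1.6-fold and 14 to 22-fold higher" than in matched controls, in that order.
- Section 1.7: in the same study, AUCinf of sofosbuvir and GS-331007 "were 2.7- and 5.5-fold higher respectively in subjects with severe renal impairment compared to matched controls with normal renal function".
- Section 1.8: "Clinical data with SOF in severe renal insufficiency and in subjects requiring hemodialysis is limited to a single dose study in non-HCV infected subjects", with no specific safety signal identified.
- Section 1.9: "The study design allows for consistent progression (~2-3 fold increase) of GS-331007 exposure across cohorts", but also "Minimal safety data is available at these high exposures, irrespective of SOF being administered with LDV or as a single agent". Table 1-3 projects Cohort 3 by applying a severe-impairment ratio.

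**What the SAP does.** SAP 7.2.1 summarises creatinine and Cockcroft-Gault clearance, with change from baseline, at every analysis window. SAP 3.6.2 keeps all data in the analysis. SAP 7.7 plans a listing of subjects dialysed during the study. No rule links that listing to the renal summaries.

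**The concern.** The protocol's own rationale treats hemodialysis as a separate class with much higher exposure than severe impairment, but that distinction does not appear among the entry criteria. Followed as written, they allow a dialysed subject to receive 12 weeks of LDV/SOF. The documents show no repeat-dose exposure or safety data for such a subject, and section 7.5.2 allows no dose reduction. The sponsor already describes safety data as minimal at the lower, severe-impairment projection.

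The smaller, separate concern is how renal function is reported. Dialysis lowers serum creatinine, and Cockcroft-Gault clearance is inversely proportional to creatinine. A subject who loses renal function and starts dialysis on study may therefore look less impaired in the eGFR change table than is true. Section 1.5.2 already draws a conclusion of stable renal function from eGFR, so the measure is used for interpretation.

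**Working it through.** **1. Does a dialysed subject meet 5h?** Take an assumed man of 60 years and 68 inches. IBW = 50 + 2.3 × 8 = 68.4 kg. Clearance = (140 − 60) × 68.4 / (72 × Scr) = 76 / Scr. The limit of 30 mL/min is met at any creatinine of 76/30 = 2.53 mg/dL or more. At 5 mg/dL he reads 15.2. The criterion does not consider dialysis.

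**2. Reproduce the plan's figure.** Table 1-1 gives the single-dose severe/normal ratio for GS-331007 AUC as 551% (90% CI 313-968). 551/100 = 5.51, which agrees with the 5.5-fold in 1.7.

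**3. Dialysis against severe impairment (single dose).** 14/5.5 = 2.55 and 22/5.5 = 4.00.

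| Reading | Low | High |
|---|---|---|
| Point estimate, 5.5-fold | 2.55 | 4.00 |
| Fold higher read as 1 + fold: 15/6.5, 23/6.5 | 2.3 | 3.5 |
| 90% CI of severe ratio: 14/9.68, 22/3.13 | 1.4 | 7.0 |
| The 1.6-fold of 1.6.1: 14/1.6, 22/1.6 | 8.8 | 13.8 |

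The last row is not used. The 1.6-fold conflicts with both 1.7 and Table 1-1, and it would make the concern look larger. The 14-22 fold has no interval and no named parameter, so 1.4-7.0 still understates the uncertainty.

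**4. Scale to Cohort 3.** If the single-dose ratio holds at steady state (assumption), the projected GS-331007 AUCtau of 111,000 ng·hr/mL becomes 111,000 × 14/5.5 = about 283,000 to 111,000 × 4.0 = 444,000. That is 9.1-14.3 times the observed Cohort 1 mean of 31,100.

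**5. Ordinary spread among undialysed subjects.** Assume a lognormal with Cohort 1's CV of 53.9%: σ² = ln(1 + 0.539²) = 0.255. P(exceeding 2.55 times the mean) = 1.8%, or 0.27 of 15. P(exceeding 4 times the mean) = 0.14%.

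**6. Dialysis started on study (all inputs assumed).** Baseline clearance is 15, true clearance falls to 8, and dialysis then cuts creatinine by 30% or 60%.
- Reading: 8/0.7 = 11.4 or 8/0.4 = 20.0.
- Recorded change: −3.6 or +5.0, against a true −7.
- A gain appears only if the cut exceeds 1 − 8/15 = 46.7%. Below that, the decline is masked in part.
- Error in a mean of 15 if the values are kept: (11.4 − 8)/15 = 0.23 to (20 − 8)/15 = 0.80 mL/min.
- Error if they are dropped, the other subjects being stable: 7/15 = 0.47 mL/min.

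**The case against.** **Other safeguards exist.** The declared population is severe renal insufficiency, which 1.6.1 separates from end-stage disease on hemodialysis. The sponsor reviews every eligibility worksheet (6.2.1). Inclusion 10 and exclusion 16 let an investigator refuse. These may well keep dialysed subjects out, but they are discretionary. The schedule also provides for anuric subjects in its pregnancy-test footnote, which suggests very advanced disease was foreseen. If dialysed patients are wanted, the protocol should say so and justify the exposure.

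**The multiple is soft.** This stands. It divides an unlabelled figure by one with a wide interval. Severe/normal AUC moved from 551% after a single dose to 817% at steady state (Table 1-1). The populations differ, so this does not isolate the effect of repeat dosing, but it does not show that ratios carry over.

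**Stronger readings that the documents do not support:**
- *All repeat-dose data come from undialysed subjects.* This is documented for Cohort 1 only. Cohort 2's dialysis status is not given, and its data are reviewed before Cohort 3 starts.
- *Exceeding the planned 2-3 fold step marks out a dialysed subject.* The step lies between cohort means. Cohort 2 is expected at 2 × 31,100 = 62,200, so the top of the step is 3 × 62,200 = 186,600, or 1.68 times the Cohort 3 mean. By the lognormal in step 5, about 10% of undialysed subjects (1.5 of 15) would pass it.
- *Dialysis will be counted as a renal gain.* Only if creatinine falls below baseline. Otherwise a decline is masked.
- *Post-dialysis values should be dropped.* That removes a decline tied to the outcome itself, and the error of 0.47 lies inside the 0.23-0.80 from keeping them. The SAP's rule for hemolyzed samples is a weak precedent, because hemolysis is a specimen defect.

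The renal event is also not lost. Dialysis is listed (16.2.8.4), individual creatinine and eGFR are listed (16.2.8.1.6.1), and the worst grade is kept (SAP 7.2.2.2). One limit is that a subject already above 6.00 mg/dL (Grade 4) at baseline cannot show a treatment-emergent rise in grade.

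**Conclusion.** The eligibility gap is real and worth closing as a cheap improvement. A dialysed subject can be dosed under the written criteria, at a GS-331007 exposure perhaps 2.5-4 times that of severe impairment (1.4-7.0 allowing for the interval of the severe ratio). This rests on three assumptions: that the unlabelled 14-22 fold refers to GS-331007 AUC, that 5.5-fold is the right severe-impairment figure, and that the single-dose ratio transfers to steady state. It does not show that a dialysed subject was or will be enrolled, or that the higher exposure is harmful.

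The reporting point is minor. In the assumed example one subject moves the mean of 15 by less than 1 mL/min. What matters is that a reader of the summary table could misread a subject in renal failure as stable or improved.

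**What to change.** **Protocol 4.3:** exclude subjects on dialysis at Screening or Day 1. This costs one amendment line needing authority and IRB/IEC approval (9.2.1) and a slightly smaller recruitment pool. It helps only while Cohort 3 enrols, because Cohorts 1 and 2 are already reported (SAP 1).

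**SAP 7.2.1:** keep the planned creatinine and Cockcroft-Gault summaries with all values. In tables 15.11.6.2.5 and 15.11.6.2.6, print the number of subjects who started dialysis on study, and show change from baseline with and without values from the start of dialysis onward. This needs a dialysis start date, assumed to be in the data behind the SAP 7.7 listing, and a little programming. It can be added before the SVR12 database is finalised, or documented in the study report if later.
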